Prior to the study the PI will ask the unit manager of the three intervention units to identify two nurse champions (to cover both nursing shifts). The PI will emphasize that the nurse champions must be

volunteers, in order to support their right to refuse without losing any job standing, as well as to support the success of the study. The PI will meet with the prospective nurse champions in private, explain the purpose of the study, procedures, possible risks and benefits, time commitment, compensation, privacy/confidentiality, payment, PI contact information, and voluntary nature of the research, including the interview that will be conducted at the end of the study. If the nurse declines to participate as champion, another potential participant will be recruited and asked to provide an informed consent. A total of six nurse champions will be recruited.

At the end of the study at each of the three hospital cites, the PI will attend a staff meeting on the three intervention units. The PI will explain the plan for focus groups to obtain nurses' feedback on the effectiveness and sustainability of the intervention. Staff nurses will receive information on the focus groups and asked to participate. The nurses will receive information about the purpose, procedures, possible risks and benefits, time commitment, compensation, privacy/confidentiality, payment, PI contact information, and voluntary nature of the research

All participants will receive a copy of the consent to keep for future reference.

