#### SITE Procedures (These procedures are repeated for Sites 1, 2 and 3.)

**Pre-intervention**: Baseline setting (census, ownership, etc.) as well as an environmental and policy information will be collected by the research evaluator on the two study units. The units will be randomized into treatment or control arm. Nurse champions (two per the intervention unit) will be recruited and consented.

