**Nurse Champion Interviews**: For the exploratory aim of assessing the cultural appropriateness of the intervention, the six nurse champions (intervention units) will be consented and interviewed, using a semi-structured interview guide, after the study ends in his/her particular unit/setting to provide their perspective. Qualitative content analysis of audiotaped, transcribed interviews will be conducted. The research evaluators will be trained to conduct these interviews.

**Staff Nurse Interviews**: Staff nurses will also be recruited at the end of the intervention at each study site, to participate in a focus group to determine their views on the effectiveness and sustainability of the intervention. We anticipate having 6-8 nurses per site (representing all three intervention units). This number is based upon our past experience recruiting for focus groups in this type setting, and the expected number to reach data saturation. However, if more than nurses volunteer/ want to participate, and/or the responses indicate the need to elicit more participation, we will add focus groups at the site. The PI and a member of the research team will conduct these interviews.

Family CG interviews: For the exploratory aim of assessing the cultural appropriateness of the intervention, we will recruit *family CGs* who self-identify as black, Latino, Asian and white, randomly selected from the Fam-FFC (intervention) sample. Approximately 10 percent of families from each ethnic group represented in the study will be approached for consent for participation in these interviews. Qualitative content analysis of audiotaped, transcribed interviews will be conducted at the six-month post-hospital discharge visit. A draft semi-structured interview guide will be refined with the input of a hospital patient /family council. Additional COVID-19 questions be asked during interview of the family CG. The research evaluators will be trained to conduct these interviews.

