## 7.4 Test Article(s) (Study Drug(s) and/or Study Device(s))

#### 7.4.1 Description

Provide a brief description of all test articles (drugs (including any foods and dietary supplements), devices and/or biologics used in the research including the purpose of their use and their approval status with the Food and Drug Administration (FDA). Include information about the form of the drug product (e.g., tablets, capsules, liquid).

The **experimental condition**, Fam-FFC, will be coordinated and implemented by a Family-centered Function Focused Care Nurse (Fam-FFC Nurse), who will work in the treatment units 20 hours a week for 14 months to implement the four components of the intervention. In addition, the sites will identify two members of the nursing staff from each unit (one for day and one for evening shift) to be Family-centered Function Focused Function Focused Care Champions (Fam-FFC Champions). The four components of Fam-FFC include: **Component I-** Environmental and Policy Assessments; **Component II-** Education and Training of Nursing Staff; **Component III-** Ongoing Training and Motivation of Nursing Staff. The Fam-FFC Nurse will work with the champions to mentor and motivate nursing staff (RN, LPN, nursing assistants) to provide Fam-FFC by: (a) role modeling Fam-FFC, reinforcing performance of and benefits of Fam-FFC, and brainstorming about ways to overcome challenges; (b) highlighting staff role models and

positive opinion leaders; and (c) eliminating the influence of negative opinion leaders; **Component IV** Implementation of the FamPath Care Pathway which includes: (a) information on the admitting condition, diagnostics, and treatment, (b) family/patient education, (c) transitional hand-off to post-acute providers, and (d) post-acute follow-up to provide ongoing education and modification of the function-focused care plan.

The Attention Control condition (Fam- FFC Ed-only) consists of Component II, education of the nursing staff in participating hospital units (exactly as offered in treatment sites), and education of CGs about hospital orientation and reinforcement of discharge teaching (medications/treatments, medical follow-up). Research staff not familiar with Components I, III and IV will deliver the staff and CG education per manualized protocol.

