# 8.0 Subject Numbers and Statistical Plan

#### 8.1 Number of Subjects

Indicate the total number of subjects to be accrued.

If applicable, distinguish between the number of subjects who are expected to be enrolled and screened, and the number of subjects needed to complete the research procedures (i.e., numbers of subjects excluding screen failures.)

We expect to screen 1000 dyads (patients/caregivers) and enroll 458-468.

We plan to enroll ten nurse champions (2 per intervention unit, a high estimate with a plan for replacement if needed).

We plan to enroll approximately 6-8 nurses for focus groups from each intervention unit at the conclusion of the intervention, with a high estimate of a total of 35 nurses. This number is based upon our past experience recruiting for focus groups in this type setting, and the expected number to reach data saturation. However, if more than nurses volunteer/ want to participate, and/or the responses indicate the need to elicit more participation, we will add focus groups at the site.

We will oversample by 20-30 patients in order to continue promoting diversity.

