Assessment of the cultural appropriateness of Fam-FCC for diverse families in our sample: We employ the Ecological Model (EM) originally developed by Bernal and colleagues as a framework to assess the cultural appropriateness of the Fam-CC intervention and to refine Fam-FCC for future studies. See below for analysis plan.

EM Model Component	Sample/Data Source	Analysis
I. Family-CG experiences of EM model constructs (categories 1,3,4,5,6,8)	Caregivers who self-identify as black, Latino, Asian and white will be randomly selected (Approximately 10% of families from each ethnic group; if theoretical saturation is not reached, interviews will continue until saturation is reached.) A draft semi-structured interview guide will be refined with the input of a hospital patient /family council.	Qualitative content analysis of audiotaped, transcribed interviews conducted at the six-month post-hospital discharge contact. Trustworthiness  is enhanced by the team's methodological expertise, random sampling, rigorous analytic approaches, member checking, and a detailed audit trail.
II. Nurse champion experiences of EM model constructs (categories 1,3,4,5,6,8)	The six champions (2 per setting) will be interviewed using a semi-structured interview guide.	Qualitative content analysis of audiotaped, transcribed interviews at conclusion of intervention at each site.
III. Evaluation of measures for reliability and validity for the ethnic groups represented in the study (category 7)	1)The internal consistency of the caregiver outcome measures as well as relationships with known correlates (e.g., educational level) will be evaluated in the first 20 Spanish-speaking respondents and 2) Both content and face validity of each measure will be discussed in participant interviews outlined in Component I above.	Cronbach's alphas for caregiver outcomes will be assessed.  The participants will be asked to assess their perceptions of measures and identify potential cultural gaps in measurement content in Component I above.
IV. Assessment of whether ethnic concordance moderates the relationship between treatment group and patient/ family outcomes (category 2).	The ethnicities of nurse champions and each family will be documented as concordant or not.	Concordance will potentially be used as a covariate in analyses for specific aims 1, 2.

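### Champion–family ethnic concordance is undefined for control families, and the covariate use proposed for Aims 1 and 2 would not test moderation and could change what GROUP estimates

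*Combined protocol and SAP*

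**What the plan says.** The table that closes section 8.3 serves the Exploratory Aim. Its component IV sets out to learn whether ethnic concordance alters the relation between treatment group and patient or family outcomes. The data source is: "The ethnicities of nurse champions and each family will be documented as concordant or not". The analysis entry reads: "Concordance will potentially be used as a covariate in analyses for specific aims 1, 2". Component IV names no GROUP x concordance term and no analysis within one arm. It gives no rule for control families, does not say which of a unit's two champions counts, and does not say whether the family's ethnicity is the patient's or the caregiver's.

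Several sections place the champions on intervention units only:
- Section 7.2, SITE Procedures: "Nurse champions (two per the intervention unit) will be recruited and consented".
- Section 5.2.1: "the PI will ask the unit manager of the three intervention units to identify two nurse champions", and then "A total of six nurse champions will be recruited".
- Section 7.2, Nurse Champion Interviews: "the six nurse champions (intervention units) will be consented and interviewed".
- Section 8.1 gives a different total but the same location: "We plan to enroll ten nurse champions (2 per intervention unit, a high estimate with a plan for replacement if needed".

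Section 7.4.1 has the looser phrase "the sites will identify two members of the nursing staff from each unit", but it stands inside the description of the experimental condition. The same section limits the control condition to staff education and caregiver education.

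The Aim 1 paragraph of section 8.3 names GROUP, TIME and SITE as the main terms, adds covariates found in baseline analyses, and tests TIME x GROUP. Aim 2 uses a similar model. Concordance is not mentioned in either paragraph.

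**The concern.** Actual concordance with a champion on the family's own unit is a feature of Fam-FFC as delivered. It is not a baseline characteristic that both arms share. Two problems follow.

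First, the stated question and the stated analysis do not match. Moderation is an interaction between treatment and the modifier, whereas a covariate contributes only a main effect.

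Second, a variable that takes the value 1 only in the treated arm splits the treatment effect between its own coefficient and GROUP. If it entered the Aim 1 and 2 models in that form, GROUP would no longer be the randomised comparison of all Fam-FFC families with all controls.

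**Working it through.** **1. Do control units have champions?** Three intervention units x 2 = 6, which reproduces the total in section 5.2.1. Champions on all six study units would number 6 x 2 = 12. The ten in section 8.1 is described as a high estimate that allows for replacement, still at two per intervention unit. Control units therefore have none.

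**2. Can own-unit concordance be tested as a moderator?** Let C = 1 for a concordant family and 0 otherwise, with every control coded 0. Then C = GROUP x C for every dyad, and the design matrix [1, GROUP, C, GROUP x C] has rank 3 of 4. The interaction cannot be separated from the main effect of C. If controls are coded missing, a complete-case fit has no control arm and GROUP cannot be estimated.

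**3. What does GROUP estimate when C (0 in controls) is a covariate?** Let p be the concordant share in Fam-FFC, and let tc and td be the effects in concordant and non-concordant families. The documents give none of these, so all are assumptions.
- Randomised contrast: p x tc + (1 − p) x td.
- GROUP with C in the model: td, when concordance is unrelated to prognosis.

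With p = 0.5, tc = 0.4 SD and td = 0.1 SD, the overall effect is 0.5 x 0.4 + 0.5 x 0.1 = 0.25 SD, and GROUP is 0.10 SD.

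A large-sample least-squares check with tc = 0.5 and td = 0.2 agrees:

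| p | Overall effect | GROUP with C |
|---|---|---|
| 0.20 | 0.26 | 0.199 |
| 0.35 | 0.305 | 0.202 |
| 0.50 | 0.35 | 0.196 |

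**4. What if the effect is the same in everyone?** Take a true effect of 0.30 SD, p = 0.35, and would-be concordant families in both arms that differ in prognosis by a. GROUP becomes 0.30 − a x p. For a = +0.2 this is 0.30 − 0.07 = 0.23, and for a = −0.2 it is 0.37. The coefficient of C (about +0.20 or −0.20) then reflects prognosis only.

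**5. What happens to precision?** There are 219 dyads per arm (3 x 73). Assume total variance 1 and the same p on each intervention unit:

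Var(GROUP) = 2 x ICC/3 + ((1 − ICC)/219) x (1/(1 − p) + 1), compared with the same expression at p = 0.

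| ICC (assumed) | Variance without C | SE ratio, p = 0.25 | p = 0.50 | p = 0.75 |
|---|---|---|---|---|
| 0 | 0.00913 | 1.08 | 1.22 | 1.58 |
| 0.01 | 0.01571 | 1.05 | 1.13 | 1.37 |
| 0.05 | 0.04201 | 1.02 | 1.05 | 1.14 |

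The unit-level part, 2 x ICC/3, is not affected by a covariate that varies within units, so clustering dilutes the loss.

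**6. Is there a version that works?** Each hospital contributes one Fam-FFC and one control unit. If every family in both arms is compared with its own hospital's intervention-unit champions, concordance exists in both arms. The matrix then has rank 4 of 4. Adding this variable leaves GROUP unchanged (0.307 with and without it, where the overall effect is 0.305).

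**The case against.** The best defence has four parts.

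**The question may be answerable.** A reader might infer that concordance can never be examined as a moderator in this trial. The documents do not support that. Component IV refers to each family and does not limit matching to the family's own unit, so control families could be matched to their hospital's champions. This stands, and step 6 shows that it works. However, the plan does not define concordance that way, and even then a covariate main effect would not test moderation.

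**H1–H3 are not committed to this model.** A reader might also infer that the main hypotheses will be tested on the wrong contrast. The Aim 1 and 2 paragraphs do not list concordance, the table is exploratory, and the use is only potential. Harm requires that concordance enters those models and that controls are coded 0. This stands as a limit. It does not remove the point, because the table names the Aim 1 and 2 analyses and leaves the choice open.

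**TIME x GROUP is better protected.** If concordance enters only as a main effect, the difference in slopes should move little. That narrows the harm for Aim 1. It helps less for Aim 2: caregiver outcomes start after discharge, with no pre-treatment value, so GROUP carries the early difference. Letting concordance act over time would redefine TIME x GROUP as well.

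**The other harms are smaller than they look.** Coding controls as missing would remove the whole control arm, which would be obvious at the first fit and is not a likely silent error. The SE increases of 8%, 22% and 58% at ICC 0 do not carry over to a trial randomised by unit. Ethnicity-by-treatment interactions, defined in both arms, are already under consideration in the Aim 1 paragraph, so less is lost by restricting concordance.

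**Conclusion.** The point holds as a gap in specification with a conditional risk to the treatment estimate. Three parts do not depend on assumed numbers: own-unit concordance is undefined for control families, the named analysis does not test the stated question, and coding controls 0 makes GROUP the comparison of non-concordant Fam-FFC families with all controls.

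The size does depend on assumptions. The illustration of 0.10 SD against 0.25 SD rests on assumed effects of 0.4 and 0.1 SD with half of families concordant. The precision loss of about 2% to 37% rests on 25–75% concordant, an ICC of 0.01–0.05, equal shares across units and 219 dyads per arm. The change in what GROUP means is the main issue, and precision is secondary.

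**What to change.** Add a sentence to section 8.3 stating that concordance with champions will not enter the Aim 1 and 2 models that test H1–H3. Then rewrite component IV in one of two ways:

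- **(a) Within Fam-FFC only.** Compare concordant with non-concordant families and report the result as a descriptive association.
- **(b) Both arms.** Define concordance for every family against the intervention-unit champions of its own hospital. Test GROUP x concordance in a separate exploratory model with site and family-ethnicity terms.

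Under either option, state whose ethnicity represents the family, how two champions of different ethnicity are handled, and what happens when a champion is replaced.

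The cost is a few lines of text. Option (a) needs no new data. Option (b) uses the champion and family ethnicities that component IV already plans to document, provided that control families are included.

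The drawback is the same for both. With about six champions, concordance is largely determined by site and family ethnicity, so once those are adjusted for, little beyond the site-by-ethnicity pattern is left to identify it. The result will be imprecise and should be labelled exploratory.

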# 9.0 Confidentiality, Privacy and Data Management

For research being conducted at Penn State Hershey or by Penn State Hershey researchers only, the research data security and integrity plan is submitted using "HRP-598 – Research Data Plan Review Form Application Supplement", which is available in the Library in CATS IRB (http://irb.psu.edu). Refer to Penn State College of Medicine IRB's "Standard Operating Procedure Addendum: Security and Integrity of Human Research Data", which is available on the IRB's website. In order to avoid redundancy, for this section state "See the Research"

Data Plan Review Form" in section 9.0 if you are conducting Penn State Hershey research and move on to section 10.

For all other research, in the sections below, describe the steps that will be taken to secure the data during storage, use and transmission.

#### 9.1 Confidentiality

//

## 9.1.1 Identifiers associated with data and/or specimens

List the identifiers that will be included or associated with the data and/or specimens in any way (e.g., names, addresses, telephone/fax numbers, email addresses, dates (date of birth, admission/discharge dates, etc.), medical record numbers, social security numbers, health plan beneficiary numbers, etc.).

If no identifiers will be included or associated with the data in any way, whether directly or indirectly, please indicate this instead.

All data will be coded with an arbitrary subject number to allow for linking of data over time. The linkage to individual names will be kept in a locked file in the project office. Additionally, we plan to follow up with post-acute visits after discharge. Thus we will collect information on the discharge date, discharge location/address, and family caregiver telephone number, and email. We will maintain a separate file of this information, which will include names and ID number, maintained in a separate file on RedCap or HIPAA-secure BOX so research evaluators can access, and a separate hard copy file in a locked cabinet in the research office.

#### 9.1.1.1 Use of Codes, Master List

If identifiers will be associated with the data and/or specimens (as indicated in section 9.1.1 above), describe whether a master record or list containing a code (i.e., code number, pseudonyms) will be used to separate the data collected from identifiable information, where that master code list will be stored, who will have access to the master code list, and when it will be destroyed.

If identifiers are included or associated with the data as described in section 9.1.1 above, but no master record or list containing a code will be used, it will be assumed by the IRB that the investigator plans to directly link the identifiers with the data.

Identifying information (name, address, telephone number, email, discharge date) along with the study ID number will be maintained in a separate master file (on secure server and locked file), not linked to the data. Only the project manager and research evaluators will have access to this information. Master files/codes will be deleted/ destroyed three years after the conclusion of the study.

#### 9.1.2 Storage of Data and/or Specimens

Describe where, how and for how long the data (hardcopy (paper) and/or electronic data) and/or specimens will be stored. NOTE: Data can include paper files, data on the internet or websites, computer files, audio/video files, photographs, etc. and should be considered in the responses. Refer to the "Investigator Manual (HRP-103)" for information about how long research records must be stored following the completion of the research prior to completing this section. HRP-103 can be accessed by clicking the Library link in CATS IRB (http://irb.psu.edu).

Please review Penn State's Data Categorization Project for detailed information regarding the appropriate and allowable storage of research data collected according to Penn State Policy AD71. Although the IRB can impose greater confidentiality/security requirements (particularly for sensitive data), the IRB cannot approve storage of research data in any way or using any service that is not permissible by Penn State Policy AD71.

The RedCap system, an electronic system used by universities worldwide, will be used for both data entry and data storage. The RedCap system will be accessed via the Penn State Clinical and Translational Science Institute (CTSI). RedCap is HIPAA compliant, with all data stored on a secure server, and encrypted. Data entry modules and stored data access is password protected and based on the individual's role on project. RedCap provides logging and audit trails on all data interactions. Consents and enrollment tracking, and contact information will be stored on a secure server (HIPAA compliant Box or RedCap) Hard copies of data will be stored in a locked cabinet in a locked office. We will store data for six years.

Consistent with NIH's Certificate of Confidentiality, the researchers will not disclose or use information, documents, or biospecimens that may identify subjects in any federal, state, or local civil, criminal, administrative, legislative, or other action, suit, or proceeding, or be used as evidence, for example, if there is a court subpoena, unless study subjects have consented for this as participants about the protections afforded by the Certificate and any exceptions to that protection. Information, documents, or biospecimens will not be disclosed to anyone else who is not connected with the research except, if there is a federal, state, or local law that requires disclosure (such as to report child abuse and neglect, elder mistreatment, harm to self or others, or communicable diseases but not for federal, state, or local civil, criminal, administrative, legislative, or other proceedings), if subjects have consented to the disclosure, including for medical treatment; or if it is used for other scientific research, as allowed by federal regulations protecting research subjects.

The researchers will comply with requests for information from personnel of the National Institute of Health which is funding this project.

The audio recording is uploaded into PSU BOX (approved for PHI) immediately and then transferred to the transcription service. Within 72 hours, the transcription is reviewed for accuracy and the recording is deleted from the device. The transcriptions will be destroyed 6 years after the completion of this evaluation.

